### **Inclusion/Exclusion Criteria:**

In Step 1, potential participants must be MSM and transgender women, have sex with men, HIV status, at high-risk for HIV acquisition. Each potential participant must have the ability and willingness to provide informed consent for study participation, including being tested for HIV-1. If HIV infection is not diagnosed, he must be willing to be enrolled in Step 2, and if diagnosed with acute or recent HIV infection be willing to consider participation in Step 3. In particular, if they are HIV seronegative on antibodies analysis, but with evidence of acute infection (HIV-1

RNA-positive confirmed by HIV antigen analysis), they should be willing to be re-contacted for further HIV testing and linkage to care.

In Step 2, volunteers who were found to have no HIV infection from Step 1 will be re-tested at variable times for incident HIV-1. Roughly, we anticipate testing 800 MSM and transgender women per month and follow-up until July 2015.

In Step 3, men with acute or recent HIV-1 infection detected at Step 1 or Step 2; or individuals who have been diagnosed with HIV in any health clinic or laboratory authorized by the Ministry of Health, and that have had a documented negative result in the past three months with no prior ART exposure, with normal hematological, renal and liver function, will be enrolled in a randomized clinical trial for immediate vs. deferred ART, unless ART initiation criteria are met earlier.

**Treatment Regimen:** In Step 1 and Step 2, no study treatment is offered. All participants will receive standard risk reduction counseling, condoms, and management of STIs. In Step 3, subjects will receive treatment as described above.

Two ART regimens are available:

- STRIBILD, co-formulated elvitegravir/cobicistat/emtricitabine/tenofovir disoproxil fumarate
- ATRIPLA,emtricitabine/tenofovir,DF/efavirenz

Co-formulated elvitegravir/cobicistat/emtricitabine/tenofovir disoproxil fumarate will be the preferred regimen for newly enrolled participants because of the early benefit of integrase inhibitors on the decline of plasma viraemia and co-formulated emtricitabine/tenofovir DF/efavirenz will be an alternative regimen. Participants who have already initiated therapy with emtricitabine/tenofovir DF/efavirenz will continue on this regimen unless they develop clinical indications warranting change in medication.

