The anti-retroviral medications available have their actions at distinct stages of the viral cycle. Integrase inhibitors act before viral integration into host DNA, reverse transcriptase inhibitors and protease inhibitors act later in this cycle. Both integrase inhibitor based regimen (Stribild: co-formulated elvitegravir/cobicistat/emtricitabine/tenofovir disoproxil fumarate) and NRTI based regimen (Atripla: co-formulated emtricitabine/tenofovir DF/efavirenz) result in high rates of viral suppression and increases in CD4 cell count. But patients receiving elvitegravir/cobicistat/emtricitabine/tenofovir exhibit a more rapid decline in HIV-1 RNA and a greater proportion had viral load suppressed to less than 50 copies/ml as compared to patients receiving emtricitabine/tenofovir DF/efavirenz. Both these regimens have once daily dosing but faster rates of viral suppression and comparatively favorable safety profile make co-formulated

elvitegravir/cobicistat/emtricitabine/tenofovir a preferred option for initiation of treatment during acute HIV infection.

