in any health clinic or laboratory authorized by the Ministry of Health, and that have had a documented negative result in the past three months, will be enrolled in a 48-week randomized, open-label clinical trial of the effects on the decay dynamics of HIV viral load in plasma, semen and rectal secretions of immediate –ARM 1- vs. deferred (by 24 weeks) –ARM 2- ART, unless ART initiation criteria are met earlier. We expect that approximately 200-250 MSM and transgender women (roughly 100-125 with acute and 100-125 with recent HIV-1 infection) will participate in the study. Those participants, who have started their participation in the study before the approval of **Amendment Letter #1** in this study protocol, will continue their participation as originally programmed. Once the **Amendment Letter #1** is approved for this study protocol, the participants who are eligible for Step 3 will be given treatment the following way: 1) those people diagnosed with **acute HIV infection** will be offered immediate ART (just at time of the enrollment visit or during the next 48 to 72 hours) for the duration of 48 weeks. 2) The people who are diagnosed with **recent HIV infection** randomized to start immediate ART or defer ART initiation until 24 weeks after HIV diagnosis, all of them followed for 48 weeks after which they will continue ART from other sources. Roughly half of these participants have been enrolled to date. These participants will receive Atripla as study drug; participants enrolled after approval of this protocol version will receive Stribild.

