#### **11.5.3 The Impact of Immediate and Early (6 Months after Diagnosis) Antiretroviral Therapy on the Decay Dynamics of HIV Viral Load**

For men with acute/recent infection plasma VL will be measured at 0, 1, 2, 4, 6, 8, 12, 16, 24, 36 and 48 weeks. Semen specimens and rectal secretions will be collected from all men with acute/recent infection at 0, 1, 2, 4, 6, 8, 12, 16, 24, 36 and 48 weeks and stored. Semen HIV VL will be measured in these samples from 60 (30 acute/30 recent) ART-treated men and 60 (30 acute/30 recent) untreated men using established procedures in the University of Washington Virology Laboratory [177, 178]. This sample size is adequate to detect a 1.0-1.5  $\log_{10}$  change in VL associated with ART based on the following: semen viral load peaks about 30 days after infection, with mean 4.5 and standard deviation 1.6 ( $\log_{10}$  copies/ml) [185]. We compute the power of a two-sample t-test comparing two arms (ART vs. no ART) to detect significant difference with type I error 5%. With 30/group we have 66% power to detect a 1.0  $\log_{10}$  change and 94% power to detect a 1.5  $\log_{10}$  change based on a single viral load measure at peak per subject. The power would be greater if we use any summary measure of individual's multiple viral loads, e.g., mean across different time points.) We will seek separate funding to analyze additional samples, including rectal secretions. VL in semen and rectal secretions will be more informative for modeling the potential impact of ART on infectivity during this period than plasma VL as these 3 measures are only modestly related [177, 178].

The viral load trajectory will be plotted for each subject and for plasma, semen and rectal secretions separately. The mean trajectory and its confidence interval will be computed stratified by randomized arm and by acute or recent infection. The first-order rate of decay, the area under the curve, the peak viral load, and the lowest viral load will be computed for each subject and compared across arms. Multiple testing adjustment will be applied to control type I error.

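### The decay analysis has no term for enrolment period or regimen, so the acute and pooled immediate-versus-deferred contrasts can mix ART timing with calendar period and drug; the randomised recent comparison is not affected

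*Combined protocol and SAP*

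**What the plan says.** - **Drug by enrolment date.** Section 4.1, on Step 3 accrual: "Roughly half of these participants have been enrolled to date". It continues: "These participants will receive Atripla as study drug; participants enrolled after approval of this protocol version will receive Stribild". The Summary (Section 2) makes Stribild the preferred regimen for new participants, keeps Atripla as an alternative, and adds: "Participants who have already initiated therapy with emtricitabine/tenofovir DF/efavirenz will continue on this regimen unless they develop clinical indications warranting change in medication".
- **The drugs are expected to differ on the outcome.** Section 3.2 says that "patients receiving elvitegravir/cobicistat/emtricitabine/tenofovir exhibit a more rapid decline in HIV-1 RNA" compared with Atripla. The Summary prefers Stribild "because of the early benefit of integrase inhibitors on the decline of plasma viraemia". Primary objective 1 concerns the decay dynamics of viral load.
- **Allocation changed too.** After Amendment Letter #1, participants with acute infection "will be offered immediate ART (just at time of the enrollment visit or during the next 48 to 72 hours" of it (Sections 2, 4.1 and 6.3.1.1). Only those with recent infection are then randomised to immediate or deferred ART.
- **Analysis.** Section 11.5.3: "The mean trajectory and its confidence interval will be computed stratified by randomized arm and by acute or recent infection". First-order decay rate, area under the curve, peak and lowest viral load are then compared across arms. Nowhere in Section 11 is there a stratum, covariate or sensitivity analysis for regimen or enrolment period.

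**The concern.** Two changes happen during enrolment: the drug, and the way acute cases are allocated. Either could be handled, but together they tie arm to period and drug within the acute stratum. Deferred acute participants can come only from before the amendment, while immediate acute participants keep accruing after it and, once the drug changes, on Stribild.

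The plan does not say how post-amendment acute participants enter the arm comparison. If they join the immediate arm, a difference in decay rate, area under the curve or lowest viral load between immediate and deferred ART reflects three things at once: timing of ART, calendar period, and drug. The last is one that the protocol itself expects to affect decay. Because nothing is prespecified, the handling would be chosen after the data are seen.

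**Working it through.** **1. The plan's own power figure.** Section 11.5.3 gives 30 per group, SD 1.6 log10, type I error 5%, two-sample t-test, with 66% power for 1.0 log10 and 94% for 1.5 log10. The noncentrality is d / (1.6 × √(2/30)), which is 2.42 for d = 1.0. With 58 df, two-sided, power is 66.3% and 94.6%. The stated figures are reproduced and not in dispute.

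**2. Regimen mix by arm.** Inputs from the documents: about half enrolled before the drug change; all acute cases offered immediate ART after the amendment; recent cases randomised throughout. Assumptions: uniform accrual, equal numbers of acute and recent cases, 1:1 randomisation, drug set by enrolment date, post-amendment acute cases counted as immediate, and both changes at 50% of enrolment.

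Per 100 acute and 100 recent participants:

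| Group | Atripla | Stribild | Stribild share |
|---|---|---|---|
| Acute, immediate | 25 | 50 | 50/75 = 67% |
| Acute, deferred | 25 | 0 | 0/25 = 0% |
| Recent, immediate | 25 | 25 | 50% |
| Recent, deferred | 25 | 25 | 50% |
| Pooled, immediate | 50 | 75 | 75/125 = 60% |
| Pooled, deferred | 50 | 25 | 25/75 = 33% |

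The gap is 67 points in acute cases, 27 points pooled, and 0 in recent cases.

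**3. Other timings.** The documents do not date the amendment relative to the drug change. Moving the drug change over 40-60% of enrolment and the amendment over 30-70%:
- The acute gap runs from 26 points (69% v 43%, drug change at 40%, amendment at 70%) to 75 points (75% v 0%, both at 40%).
- The pooled gap runs from 12 to 27 points.
- The immediate arm has the larger Stribild share in every case, and the recent gap is always 0.

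**4. Non-concurrent share, whatever the drug.** With the amendment at fraction a of enrolment, the non-randomised share of the acute immediate group is (1 − a) / (1 − a/2). This is 0.5/0.75 = 67% at a = 0.5, 0.7/0.85 = 82% at a = 0.3, and 0.3/0.65 = 46% at a = 0.7.

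**5. From mix to log10.** Distortion of an on-ART contrast is the gap in share times the regimen difference. Per 1.0 log10 of regimen difference, the base case gives 0.67 log10 (acute), 0.27 (pooled) and 0 (recent). The documents give no regimen difference, so these are multipliers and not estimates.

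**6. What handling it costs.** One regimen or period covariate, balanced between groups, takes one df: power stays at 66.3% and 94.6%. Separate tests per regimen at an assumed 15 per group would have 38.0% and 69.8%. Restricting the acute contrast to concurrently randomised participants, with 75 to 90 acute cases (Section 11.3) and the amendment at 50%, leaves 75 × 0.25 ≈ 19 to 90 × 0.25 ≈ 23 per arm. By the formula in step 1, power is then 47% to 55% for 1.0 log10 and 80% to 87% for 1.5 log10.

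**The case against.** **Mixing regimens is declared.** The Summary says the study does not compare medications, and Sections 6.3.7.3 and 9 say the target is ART in general. That stands as a reason to allow two drugs and to average over them. It does not justify crediting an unbalanced drug mix to timing.

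**Read literally, the contrast may be sound.** Section 11.5.3 stratifies by randomised arm, and post-amendment acute cases are not randomised. On that reading they drop out of the acute contrast, and if both changes coincide, everyone left in it is on Atripla. This stands as a possible reading, but the plan does not state it, and Section 7.4.2.1 still speaks of acute cases starting treatment after randomisation. The point is therefore conditional on how they are counted.

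**Early on-ART decay is barely compared between arms.** Deferred participants are generally untreated to week 24, and the next viral loads listed for them in Sections 7.4.3.8 and 11.5.3 are at weeks 36 and 48. Section 3.3.3 puts 90% of patients below 50 copies/ml four months after starting ART. This stands: regimen acts mainly through the immediate arm, and the multipliers in step 5 should not be read as expected bias in early decay.

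**Stronger readings to avoid.** A reader might infer that the whole immediate-versus-deferred comparison is confounded by drug. It is not: recent cases are randomised concurrently in both periods, so regimen is balanced between arms in expectation. A reader might also set a shift in log10 against the 1.0 log10 in the power statement. That figure is for semen viral load at peak, ART versus no ART, while the Summary's early-benefit claim concerns plasma. Acute-versus-recent decay is displayed by stratum but is not a stated test.

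**Conclusion.** The point holds in a limited form. Section 11.5.3 leaves open an arm comparison that, among acute cases and pooled over stage, would be partly non-concurrent and unbalanced in drug: 67% v 0% and 60% v 33% Stribild in the base case, with gaps of 26-75 and 12-27 points over the other timings tried. This rests on 1:1 randomisation, uniform accrual, drug fixed by enrolment date, and post-amendment acute participants being counted as immediate. The direction of the imbalance did not change over the range tried.

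The bias in log10 cannot be determined from the documents. They give no regimen effect, do not state the order of the two changes, and schedule few on-ART viral loads in the deferred arm. This is an inexpensive improvement that removes a real source of bias; it does not show that the primary comparison is invalid.

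**What to change.** In Section 11.5.3:

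1. Base the immediate-versus-deferred comparison on concurrently randomised participants: recent cases in both periods, and acute cases randomised before Amendment Letter #1. Report post-amendment acute participants separately, as a non-randomised immediate-ART group.
2. Add enrolment period (before or after the amendment, and before or after the drug change) as a stratum or covariate. Estimate arm differences within period and combine them.
3. Show trajectories and decay rates by regimen received, as a descriptive sensitivity analysis and not as separate tests.

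Separately, Sections 2 and 4.1 must be reconciled on which drug applies to deferred participants who enrolled before the change but had not yet started ART. Section 2 speaks of those who have started Atripla, Section 4.1 of those enrolled. The answer decides how regimen is coded in the deferred arm.

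Cost: plan wording and one more stratum. Enrolment is dated, and dispensing and treatment changes are already recorded (Sections 6.3.6 and 7.4.3.4). The period term costs a few degrees of freedom at most. The acute contrast becomes smaller, about 19 to 23 per arm in the base case. The number of deferred acute participants is already fixed by the amendment, so what is given up is only the non-randomised part of the immediate group.

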### **6.3 STEP 3**

#### **6.3.1 Regimens, Administration, and Duration**

##### **6.3.1.1 Regimen**

Those participants, who have initiated their participation in the study before the approval of **Amendment Letter #1** in this study protocol, will continue their participation as originally programmed.

Once the **Amendment Letter #1** is approved for this study protocol, the participants who are eligible for Step 3 will be given treatment the following way:

- Those people diagnosed with **acute HIV infection** will be offered immediate ART (just at time of the enrollment visit or during the next 48 to 72 hours) for the duration of 48 weeks.

Weeks 0-48: Co-formulated elvitegravir/cobicistat/emtricitabine/tenofovir disoproxil fumarate (or co-formulated emtricitabine/tenofovir DF/efavirenz) orally once daily.

Those people diagnosed with recent HIV infection will be randomized to one of the following arms:

1. Arm 1:

Weeks 0-48: Co-formulated elvitegravir/cobicistat/emtricitabine/tenofovir disoproxil fumarate (or co-formulated emtricitabine/tenofovir DF/efavirenz) orally once daily.

2. Arm 2:

Week 0-24: No treatment unless Peruvian criteria for initiation of treatment are met.

Week 25-48: Co-formulated elvitegravir/cobicistat/emtricitabine/tenofovir disoproxil fumarate (or co-formulated emtricitabine/tenofovir DF/efavirenz) orally once daily.

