## **7.4.2 Timing of Evaluations**

### **7.4.2.1 Entry Evaluations (Week 0 Visit)**

Subjects diagnosed with acute HIV infection must begin treatment within 72 hours after randomization, and preferably within 24 hours. Subjects randomized to Arm 1 must begin treatment within 72 hours after randomization, and preferably within 24 hours.

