#### **7.4.3.8 Virologic Studies**

1. Plasma HIV-1 RNA

All HIV-1 RNA testing will be performed using the Abbott *m2000 RealTime* System (Abbott Molecular) at the IMPACTA PERU Clinical Trials Unit Central Laboratory, which

is certified by the U.S. NIH/NIAID/DAIDS Virology Quality Assurance (VQA) Program. The baseline value will be the HIV-1 RNA level at the entry evaluation.

The results from the analysis of Plasma HIV-1 RNA for the visits 0, 12, 24, 36, and 48 will be available at the next follow-up visit to guide the medical management decision-making for each participant, according to the HIV management standards.

The plasma samples for RNA HIV-1 determination from visits 1, 2, 4, 6, 8, 16, and 20 will not be processed in real time. Since these determinations are exclusively research purposes, the samples will be processed at a later time.

2. **Phylogenetic Analyses**

HIV-1 sequencing and phylogenetic analysis will be performed at The University of Washington Molecular Genetics Laboratory

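### Section 11.5.3 compares whole-series peak viral load across arms, but week 0 counts towards it, so for recent infections this one measure greatly understates the ART effect

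*Combined protocol and SAP*

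**What the plan says.** Section 11.5.3 names four per-subject summaries: first-order decay rate, area under the curve, peak and lowest viral load. For the last two it says that "the peak viral load, and the lowest viral load will be computed for each subject and compared across arms". It gives peak no window, no exclusion of baseline and no baseline adjustment.

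The series starts at entry: "plasma VL will be measured at 0, 1, 2, 4, 6, 8, 12, 16, 24, 36 and 48 weeks", with the same weeks listed for semen and rectal samples. Section 7.4.3.8 states that "The baseline value will be the HIV-1 RNA level at the entry evaluation". Section 7.4.2.1 adds that "Subjects randomized to Arm 1 must begin treatment within 72 hours after randomization, and preferably within 24 hours". Arm 2 is untreated until week 24 and treated from week 25 (6.3.1.1).

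After Amendment Letter #1, acute cases are offered immediate ART and only recent infections are allocated at random: "Those people diagnosed with recent HIV infection will be randomized to one of the following arms" (6.3.1.1). Recent means antibody positive with a negative test in the previous 3 months (5.3.2).

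On timing and power, 11.5.3 says that "semen viral load peaks about 30 days after infection", with mean 4.5 and SD 1.6 log10 copies/ml. At 30 per group it gives 66% power for a 1.0 log10 change and 94% for 1.5 log10, "based on a single viral load measure at peak per subject". It adds that power would rise with any per-subject summary of the repeated values, giving the mean over time points as its example.

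**The concern.** A maximum can be set by a sample taken before treatment could act. If a man's viral load is already flat or falling at week 0, his maximum in Arm 1 is likely to be the week-0 value, however well ART works afterwards. In Arm 2 it is the highest of many untreated readings. The arm difference then depends mainly on measurement and biological noise and on how many untreated samples there are, and only weakly on the size of the ART effect.

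Peak is one of the four summaries that serve primary endpoint 1 (11.2.1). A small or non-significant difference in peak could be read as a weak effect of immediate ART when the true effect is large. A reader relying on the remark about any summary measure would also expect this comparison to have more than 66% or 94% power.

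**Working it through.** **1. The plan's own power.** Two-sided two-sample t-test, 30 per group, SD 1.6, alpha 5%. The standard error is 1.6 × √(2/30) = 0.413, so the noncentrality is 1.0/0.413 = 2.42 or 1.5/0.413 = 3.63, on 58 degrees of freedom. Power is 66.3% and 94.6%. The stated 66% and 94% reproduce to within a point.

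**2. Are recent infections past day 30 at week 0?** Section 3.5.1 gives an eclipse phase of 7-21 days and an RNA-to-antibody window of about 5 + 7 = 12 days. Assume that the last test was RNA negative, the eclipse is uniform on 7-21 days, and the time from first RNA to an antibody-positive visit is uniform from 12 days to the testing interval. That interval is 30 days in 7.3.1 and 3 months in 5.2.

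- 30-day testing: P(not past day 30 at diagnosis) = (11²/2)/(14 × 18) = 60.5/252 = 24%, so 76% are past it.
- 90-day testing: 60.5/(14 × 78) = 60.5/1092 = 5.5%, so 94% are past it.
- If week 0 falls 7 days after diagnosis (assumed), the numerator becomes 4²/2 = 8: 8/252 = 3% and 8/1092 = 1%, so 97-99% are past it.

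The 30-day figure is for semen. No peak day is given for plasma or rectal secretions, although 3.6.2 says that the initial viraemia usually resolves in 2 months.

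**3. What the maximum measures after the peak.** Without noise, and with viral load flat or falling, each man's maximum equals his week-0 value in both arms. The expected arm difference is zero for any ART effect. With within-man SD w and no natural decline, Arm 2 has nine untreated samples (weeks 0, 1, 2, 4, 6, 8, 12, 16, 24). The expected maximum of nine standard normal values is 1.485. When ART works strongly and the Arm 1 maximum is the week-0 value, the difference is about 1.485w: 0.45 log10 for w = 0.3 and 1.19 for w = 0.8. Natural decline lowers it. The ART effect does not enter that expression.

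**4. Simulation.** Mean 4.5, total SD 1.6, 30 per arm, the visit weeks of 11.5.3, maximum per man, t-test. The documents do not give within-man SD, natural decline or speed of ART response, so these are assumptions. Set A: w 0.3-0.8, decline 0-1.0 log10 by week 24, ART effect complete by week 4. Set B: w 0.2-0.7, decline 0 or 1 log10 after the peak, half the ART effect reached by 2 weeks, week 0 seven days after diagnosis.

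| True effect | Difference in peak, A | Power, A | Power, B | Stated power (single value) |
|---|---|---|---|---|
| 1.0 log10 | 0.21-0.57 | 7-32% | 5-27% | 66% |
| 1.5 log10 | 0.24-0.74 | 9-49% | 5-43% | 94% |

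In set B the 1.5 log10 effect gives a peak difference of 0.08-0.70. The Arm 1 peak falls at week 0 in 50-98% of men and correlates 0.95-1.00 with the week-0 value. A true 3 log10 effect still gives only 0.27-0.97 (A) or 0.08-0.93 (B).

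**5. Alternatives at a true 1.5 log10 effect.**

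- Dropping week 0 only (B): difference 0.52-0.99, power 24-71%. Weeks 1-2 are still early on ART.
- Peak within weeks 4-24 (B): 1.23-1.37, power 83-93%.
- Mean log10 over weeks 4-24 (A): the full 1.5, power 95% or more (68-78% for 1.0 log10).

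The mean loses a little if ART acts as in set B. The fraction of effect reached is 1 − 2^(−t/2), which averages (0.750 + 0.875 + 0.938 + 0.984 + 0.996 + 1.000)/6 = 0.924 over weeks 4, 6, 8, 12, 16 and 24. The expected difference is then 0.924 × 1.5 = 1.39.

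**6. Acute men randomised before the amendment.** With a uniform 0-12 days from first RNA to detection and 3 days to week 0 (assumed), P(past day 30) = (6²/2)/(14 × 12) = 18/168 = 11%, so about 89% are before the semen peak. Their maximum can carry some ART effect: 0.37-0.74 log10 for a true 1.5, with 13-45% power.

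**The case against.** The strongest reply is that the power sentence and the compared summary use different peaks. The power sentence concerns one value per man at about day 30. It does not concern the maximum of a series. A reader might infer that the semen sample size rests on the per-subject maximum and that 66% and 94% are wrong. The documents do not support that: the figures reproduce for the quantity they describe. What stands is that they say nothing about the maximum, and that the remark on any summary measure fails for it.

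A reader might also infer that the plan hides the treatment effect altogether. It does not. Decay rate, lowest value and area under the curve remain, as do mean trajectories by arm and by acute or recent infection, and primary objective 1 is about decay dynamics. In set B a time-averaged area under the curve to week 24 keeps 88-93% power at 1.5 log10, although 11.5.3 does not fix that window.

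Third, not every randomised man is past the peak. Up to 24% of recent cases may be before day 30 at diagnosis under monthly testing. Acute men enrolled before the amendment continue as originally programmed, and Section 4.1 says roughly half of participants had been enrolled. For them a peak comparison has some rationale, so it is too strong to say that ART cannot affect peak.

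Fourth, the cost in multiplicity is slight. The plan names no adjustment method. Under Bonferroni (assumed), going from four tests to three raises power from 44% to 49% at 1.0 log10 and from 85% to 87% at 1.5 log10.

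Finally, the documents do not say outright that week 0 counts. That follows from the visit list and the absence of any exclusion.

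**Conclusion.** The concern holds for whole-series peak as a between-arm measure in recent infections. A true 1.5 log10 effect would appear as roughly 0.2-0.75 log10, with about 10-50% power at 30 per arm and down to 5% under the least noise tried. These ranges rest on assumed within-man SD, natural decline and speed of ART response. The direction was the same in every scenario, and the bound in step 3 shows why. The problem is confined to one of four summaries and is milder, though still present, for acute men randomised before the amendment. The stated power is arithmetically sound for a single value at a fixed time; the extension to any summary measure is wrong for the maximum.

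**What to change.** In Section 11.5.3:

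- Report whole-series peak descriptively, by arm and by acute/recent stratum.
- Make the between-arm comparison on a fixed on-treatment window that ends before Arm 2 starts ART. Mean log10 viral load over the week 4, 6, 8, 12, 16 and 24 samples would serve; peak limited to that window is an acceptable alternative. Excluding week 0 alone is not enough.
- Reword the power text to refer to the chosen measure and drop the claim about any summary measure.

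Section 4.2 counts Arm 2's 24 weeks from diagnosis in one sentence and from enrolment in another. These must be reconciled before the last visit of the window is fixed.

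The cost is a change of wording and one changed derivation. All the samples are already scheduled, and semen and rectal assays are run at the end of the study (7.4.3.10), so the measure can be set before those results exist. The loss is the between-arm test of whole-series peak, including for the acute men in whom it carries some information.
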